6.2.4.2 Additional dosing guidelines for scheduled visit days

On days with PK, ECG sampling, chemistry and/or lipid profile sampling as outlined in [Table 7-1](#), the following additional guidelines should be followed:

- On a day when PK blood collection is scheduled at the clinic, patients must take study treatment in the clinic under the supervision of the Investigator or designee. On all other days patients may take the study treatment at home.
- The patient must be fasting for at least 8 hours prior to cycle visits that include fasting glucose and lipid profile samples. Coffee, tea and water without milk and sugar (or artificial sweeteners) are allowed.
- If a pre-dose ECG measurement should be collected, then the ECG measurement should occur before dosing of the study treatment.
- When both PK and ECG are required, please complete the ECG prior to PK draw.
- Post-dose ECGs and PKs should be collected after dosing of the study treatment. ECG will be performed according to [Section 7.2.2.6](#) and [Table 7-5](#).
- Pre-dose samples should be drawn prior to dosing. The sampling time of the PK samples and the dosing time must be precisely recorded in the eCRF.
- Post-dose PK samples should be collected after dosing of the study treatment. PK sample collection will be performed according to [Table 7-6](#).

6.3 Overview of Dexamethasone oral solution

Dexamethasone steroid-based oral solution comprised of 0.5 milligrams per 5mL of alcohol free dexamethasone. The oral solution contains citric acid, disodium edentate, flavoring, glycerin, methylparaben, propylene glycol, propylparaben, sorbitol and water.

6.3.1.1 Dexamethasone administration

All patients will be given 0.5 mg/5 mL dexamethasone steroid mouthwash. The patient will initiate the dexamethasone steroid mouthwash on the same day that they initiate the study treatment (C1D1). The alcohol-free, 0.5 mg/5 mL dexamethasone steroid mouthwash should be administered based on the following instructions:

- 10 mL of mouthwash swish and spit 3 times daily (TID). The mouthwash is to be held in mouth and swished around mouth to come in contact with entire buccal mucosa surface for a minimum of two minutes, and then spit out.
- Patient should remain NPO (no food, no drinks, nothing in mouth) for at least an hour after administering mouthwash, with the exception of Nystatin (or another topical antifungal).

6.3.1.2 Dexamethasone treatment regimen

Cycle 1 Day 1 (C1D1) is the day the patient initiates the mouthwash regimen and study drugs. A treatment cycle consists of 28 days. Patients should use mouthwash regimen for two consecutive treatment cycles (56 days).

All patients will be instructed to perform routine “good oral care” each day during the trial. Good oral care will consist of: brushing teeth at least twice daily with soft bristled toothbrush continue current daily flossing routine (if patients were not already flossing daily, they should not be instructed to start flossing as this could cause oral trauma), and continue routine dental care/maintenance with their dentist, if they have one.

Salt water mouth rinse and the steroid mouthwash should be administered based on the following instructions:

- The Salt water mouth rinse will only be administered once the onset of Grade 1 stomatitis has been noted.

If the salt water (0.9%) mouth rinse is needed, it will be administered as 10mL swish and spit TID and must be done prior to the dexamethasone mouthwash. The patient should administer the salt water (0.9%) mouth rinse (swish and spit) and wait for 10-15 minutes before administering the dexamethasone mouthwash.

The alcohol-free, 0.5mg/5mL dexamethasone steroid mouthwash should be administered based on the following instructions:

- 10 mL of mouthwash swish and spit TID. The mouthwash is to be held in mouth and swished around mouth to come in contact with entire buccal mucosa surface for a minimum of two minutes, and then spit out.
- Patient should remain NPO (no food, no drinks, nothing in mouth) for at least an hour after administering mouthwash, with the exception of Nystatin (or another topical antifungal).

6.4 Dose modification

6.4.1 Dose cohort modification

For patients who do not tolerate the protocol-specified dosing schedule, ribociclib adjustments are **recommended** in order to allow the patient to continue the study treatment.

Dose reductions are not permitted for everolimus, exemestane or GnRH agonists (if patient is currently taking). Any changes to the dose or interruption of dosing must be recorded on the Dosage Administration Record eCRF. Patients who require a study treatment hold of more than 28 days will be discontinued from the study unless discussed and approved by the sponsor ([Section 7.1.2](#)). Once dose-reduced the dose may be re-escalated once discussed and approved by the sponsor. All patients will be followed for AEs and for SAEs for 30 days following the last dose of study drug.

6.4.1.1 Ribociclib (LEE011)

Management of severe or intolerable adverse reactions requires dose reduction, temporary interruption, and/or discontinuation of ribociclib therapy. Each patient is allowed a maximum of two dose reductions for ribociclib. After this, the patient will be discontinued from the study treatment. For each patient, once a dose level reduction for ribociclib has occurred, the dose level may be re-escalated during subsequent treatment cycles once discussed and approved by the sponsor. If a dose reduction is required, ribociclib should be reduced one dose level. Dose levels for ribociclib are provided in [Table 6-5](#).

A dose-dependent DDI was observed between ribociclib and everolimus based on clinical PK analyses in a separate dose escalation trial, where everolimus exposure increased 2- to 4-fold in the presence of ribociclib. If a dose adjustment of both ribociclib and everolimus are required, a dose reduction in ribociclib is considered as a method to reduce exposure to both drugs since everolimus exposure is increased with increased ribociclib doses through a DDI. After permanent discontinuation of either ribociclib, everolimus or exemestane, patients should be discontinued from study treatment. The dose modification guidelines for study treatment are found in [Table 6-5](#) and [Table 6-6](#).

Table 6-5 Phase I dose escalation (cohort A and B) and Phase II group 1: Dose modification guidelines for Ribociclib + everolimus + exemestane

	Ribociclib	Everolimus	Exemestane
	Dose	Dose	Dose
Starting dose	Phase I: refer to cohort A, or B. Phase II cohort 1: 300mg (daily)	2.5 mg daily	25 mg
First dose reduction	Reduced by 50mg	2.5 mg daily	
Second dose reduction	Change current dose to 21days out of 28	2.5 mg daily	

Table 6-6 Phase I dose de-escalation (cohort C) and Phase II cohort 2: Dose modification guidelines for Ribociclib + everolimus + exemestane

	Ribociclib	Everolimus	Exemestane
	Dose	Dose	Dose
Starting dose	200mg daily	If starting at dose level 0: 5mg daily	25 mg

		If starting at dose level -1: 2.5mg daily	
First dose reduction	200mg daily	If starting at dose level 0: 2.5mg daily If starting at dose level -1: 2.5mg every other day	
Second dose reduction	200mg daily	If starting at dose level 0: 2.5mg every other day If starting at dose level -1: discontinue from trial	

Management of everolimus specific adverse reactions may require temporary dose reduction and/or interruption of everolimus therapy longer than 3 weeks. Recommendations for dose interruption of everolimus longer than 3 weeks in the management of everolimus specific adverse reactions are summarized in [Table 6-7](#). Clinical judgment of the treating physician should guide the management plan of each patient based on individual benefit/risk assessment ([USA Afinitor® PI 2012](#)).

Table 6-7 Dose modification guidelines for ribociclib (if everolimus is held longer than 3 weeks for pneumonitis)

	Ribociclib	Exemestane
	Dose	Dose
Starting dose	400 mg daily	25 mg
First dose reduction	200mg daily	
Second dose reduction	200mg 3 weeks on, 1 week off	

6.4.1.2 Exemestane

No specific dose modifications are recommended for exemestane. Toxicities attributed to exemestane should be managed in a manner consistent with the investigator's usual clinical practice. Per ([exemestane package insert](#)).

6.4.2 Anticipated Risks and safety considerations of the study drug combination

Preclinical and Phase I clinical data available from ongoing studies with ribociclib and everolimus with exemestane separately suggest few overlapping toxicities for the proposed combinations. Special attention will be paid to blood counts (cytopenias), mucositis, liver function test abnormalities and QTc prolongation. Clinical data from the [CLEE011X2101] study do not show marked accumulation in ribociclib with time, suggesting that it does not substantially inhibit its own metabolism or clearance. Based on the known properties of exemestane and ribociclib, a clinically significant drug-drug interaction that would increase the toxicities of either drug is not anticipated.

Everolimus and ribociclib are *in vitro* inhibitors and substrates of CYP3A4, and the latter is also a time-dependent CYP3A4 inactivator. The available preclinical and clinical data therefore suggest the possibility of a drug interaction, specifically one that may increase exposure to everolimus. Based on simulation using Simcyp software (Simcyp Version 12, release 1), the projected increase in the AUC_{0-6h} of everolimus was 3.5-fold following the starting daily dose of 200 mg ribociclib co-administered with 2.5 mg of everolimus for 14 days. No significant effect on ribociclib metabolism was predicted when co-administered with everolimus. Appropriate eligibility criteria, dose modification guidelines and stopping rules are included in this protocol.

6.4.3 Dose modifications for ribociclib+everolimus+exemestane combination

6.4.3.1 Dose modifications and management recommendations for hematologic adverse reactions

Table 6-8 Dose modifications and management recommendations for hematologic adverse reactions

(see [Table 6-5](#) and [Table 6-6](#) for dose reduction guide)

Toxicity	Grade	Dose Adjustment and Management Recommendations
Thrombocytopenia	Thrombocytopenia	
	Grade 1 ($\geq 75 \times 10^9/L$)	No dose adjustment required.
	Grade 2 ($\geq 50 \times 10^9/L - < 75 \times 10^9/L$)	Dose interruption of ribociclib and everolimus until recovery to grade ≤ 1 . Re-initiate study treatment at the same dose.
	Grade 3 ($\geq 25 \times 10^9/L - < 50 \times 10^9/L$)	Dose interruption of ribociclib and everolimus until recovery to grade ≤ 1 .

Toxicity	Grade	Dose Adjustment and Management Recommendations
		
Re-initiate study treatment at the same dose level.
 
If toxicity recurs at grade 3: temporary dose interruption of ribociclib and everolimus until recovery to grade ≤ 1 and reduce to the next lower dose level. Maintain everolimus at same dose

	Grade 4($<25 \times 10^9/L$)	
Dose interruption of ribociclib and everolimus until recovery to grade ≤ 1.
 
Re-initiate study treatment at the next lower dose level. If toxicity recurs at grade 4: discontinue study treatment

Neutropenia	Absolute neutrophil count (ANC)	
	Grade 1 ($\geq 1.5 \times 10^9/L$)	No dose adjustment required.
	Grade 2 ($\geq 1.0 - <1.5 \times 10^9/L$)	No dose adjustment required.
	Grade 3 ($\geq 0.5 - <1.0 \times 10^9/L$)	
Dose interruption of ribociclib and everolimus until recovery to $\geq 1.0 \times 10^9/L$.
 
Re-initiate study treatment at the same dose level.
 
If toxicity recurs at grade 3: temporary dose interruption of ribociclib and everolimus until recovery to grade ≤ 1 and reduce to the next lower dose level, or continue at same dose with growth-factor support at the discretion of the treating investigator.

	Grade 4 ($<0.5 \times 10^9/L$)	
Dose interruption of ribociclib and everolimus until recovery to $\geq 1.0 \times 10^9/L$.
 
Re-initiate ribociclib at the next lower dose level (first dose reduction level). Maintain everolimus at same dose
 
If toxicity recurs at grade 4: temporary dose interruption of ribociclib and everolimus until recovery to $\geq 1.0 \times 10^9/L$ and reduce at the next lower dose

Toxicity	Grade	Dose Adjustment and Management Recommendations
		level. Maintain everolimus at same dose
Febrile Neutropenia	Grade 3: ANC<1.0 x 10 ⁹ /L with [a single temperature of >38.3 degrees C (101 degrees F) or a sustained temperature of >=38 degrees C (100.4 degrees F) for more than one hour] .	Dose interruption of both ribociclib and everolimus until improvement of ANC \geq 1.0 x 10 ⁹ /L and no fever. Restart at the next lower dose level. If febrile neutropenia recurs, discontinue study treatment. Colony Stimulating Factors should be considered in patients with fever and profound neutropenia (<1.0 x 10 ⁹ /L)
	Grade 4 Life-threatening consequences; urgent intervention indicated	Discontinue study treatment
Anemia (Hemoglobin)	Grade 1: \geq 10.0 – LLN g/dL	No dose adjustment required
	Grade 2: \geq 8.0 – <10.0 g/dL	No dose adjustment required.
	Grade 3: <8.0 g/dL	Dose interruption of ribociclib and everolimus recovery to grade 1. Re-initiate study treatment at the same dose.
	Grade 4: Life-threatening consequences; urgent intervention indicated	Discontinue study treatment PRBC transfusion to be considered per NCCN guidelines

6.4.3.2 Ribociclib/everolimus dose modification and management for QTcF prolongation

Table 6-9 Ribociclib/everolimus dose modification and management for QTcF prolongation

(see [Table 6-5](#) and [Table 6-6](#) for dose reduction guide)

Adverse drug reaction	Severity	Dose adjustment and management recommendations
QTcF prolongation	For All Grades	Check the quality of the ECG and the QT value and repeat if needed.

Adverse drug reaction	Severity	Dose adjustment and management recommendations
		
Perform analysis of serum electrolytes (K+, Ca++, Phosphorus, Mg++). If outside of normal range, hold ribociclib and everolimus, correct with supplements or appropriate therapy as soon as possible, and repeat electrolytes until documented as normal.
 
Review concomitant medication usage for the potential to inhibit CYP3A4 and/or to prolong the QT interval.
 
Check compliance with correct dose and administration of study treatment
 
Consider collecting a time matched PK sample; record date and time of last study drug intake.

	Grade 1 QTc 450-480 ms	
Perform steps 1-4 as directed in "For All Grades." No dose adjustment required.

	Grade 2 QTc 481-500 ms	
Hold ribociclib and everolimus. Perform steps 1-4 as directed in "For All Grades."
 
Repeat ECG as clinically indicated until the QTcF returns to <481 ms. Restart ribociclib with dose reduced by 1 dose level.
 
If QTcF \geq 481 ms recurs, ribociclib should be reduced again by 1 dose level.
 
Repeat ECGs 7 days and 14 days after dose resumption of study treatment (then as clinically indicated) for any patients who had therapy interrupted due to QTcF \geq 481 ms.

	Grade 3 QTc \geq 501 ms on at least two separate ECGs	
Hold ribociclib and everolimus. Perform steps 1-4 as directed in "For All Grades."
 
Transmit ECG immediately and confirm prolongation/

Adverse drug reaction	Severity	Dose adjustment and management recommendations
		
abnormalities with central assessment. Perform a repeat ECG within one hour of the first QTcF of ≥ 501 ms.
 
If QTcF remains ≥ 501 ms, consult with a cardiologist (or qualified specialist) and repeat cardiac monitoring as indicated until the QTcF returns to <481 ms.
 
If QTcF returns to <481 ms, study treatment will be reduced by 1 dose level;
 
If QTcF remains ≥ 481 ms after performing steps 1-4 as directed in "For All Grades," discontinue ribociclib.
 
Repeat ECGs 7 days and 14 days after dose resumption (then as clinically indicated) for any patients who had therapy interrupted due to QTcF ≥ 501 ms
 
If QTcF of ≥ 501 ms recurs, discontinue study treatment. Perform frequent ECGs until the QTcF is <500 msec. Address electrolyte, calcium and magnesium abnormalities.

	
Grade 4
 
QT/QTc ≥ 501 or >60 ms change from baseline and
 
Torsade's de pointes or polymorphic ventricular tachycardia, or signs/symptoms of serious arrhythmia
	
Discontinue study treatment. Perform steps 1-4 as directed in "For All Grades."
 
Transmit ECG immediately and confirm prolongation/ abnormalities with central assessment. Obtain local cardiologist (or qualified specialist) consultation and repeat cardiac monitoring as indicated until the QTcF returns to <481 ms.

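### Cohort C and Phase II Group 2: three toxicity rules call for a lower ribociclib dose, but the reduction table for these patients (Table 6-6) has no ribociclib level below 200 mg daily

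*Protocol*

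**What the plan says.** Three rules lower ribociclib when treatment restarts after recovery:

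- Protocol Table 6-9, QTcF 481-500 ms: "Restart ribociclib with dose reduced by 1 dose level"; if 481 ms or more recurs, "ribociclib should be reduced again by 1 dose level".
- Protocol Table 6-8, grade 4 neutropenia: "Re-initiate ribociclib at the next lower dose level (first dose reduction level). Maintain everolimus at same dose".
- Protocol Table 6-8, recurrent grade 3 thrombocytopenia: hold both drugs until recovery, "and reduce to the next lower dose level. Maintain everolimus at same dose".

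Both tables name Tables 6-5 and 6-6 as the guide to dose levels. Table 6-6 is the one for cohort C and Phase II Group 2. Its ribociclib column reads 200 mg daily in all three rows. Its everolimus column falls; the first-reduction entry is "If starting at dose level 0: 2.5mg daily If starting at dose level -1: 2.5mg every other day".

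Section 6.4.1.1 adds "Each patient is allowed a maximum of two dose reductions for ribociclib" and refers to Table 6-5 for the ribociclib levels, but that table's title is "Phase I dose escalation (cohort A and B) and Phase II group 1: Dose modification guidelines". Section 6.4.1 recommends ribociclib adjustments and bars everolimus reductions. The text after Table 6-6 nevertheless allows temporary everolimus reduction for everolimus-specific reactions.

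**The concern.** A site treating a Group 2 patient has a toxicity rule that orders a ribociclib step and a group-specific table that contains none. The patient can then be restarted on the ribociclib dose that preceded the event. The protocol relies on the missing step: Section 6.4.1.1 says "a dose reduction in ribociclib is considered as a method to reduce exposure to both drugs", and the Amendment 3 rationale gives ribociclib reduction at the first QTcF of 481 ms or more as its first purpose, because the QT effect depends on ribociclib concentration. Lowering everolimus is no substitute, since Section 2.1.1 states that ribociclib exposure does not change when everolimus is given with it.

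**Working it through.** No sample size or error rate is involved. The check sets the rules against the table and looks for any other provision that gives these patients a lower ribociclib level.

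**Step 1. Reduction levels (Section 6.4.1.1).**

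| | Table 6-5, Group 1 | Table 6-6, Group 2 (dose level 0) |
|---|---|---|
| Start | ribociclib 300 mg, everolimus 2.5 mg | ribociclib 200 mg, everolimus 5 mg |
| First reduction | ribociclib 300 - 50 = 250 mg, everolimus 2.5 mg | ribociclib 200 mg, everolimus 2.5 mg |
| Second reduction | current ribociclib dose on 21 of 28 days, everolimus 2.5 mg | ribociclib 200 mg, everolimus 2.5 mg every other day |
| Ribociclib levels below start | 2 | 0 |

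**Step 2. Apply each rule to a Group 2 patient on 200 mg + 5 mg.**

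- Grade 4 neutropenia: the ribociclib entry at first reduction is 200 mg, and Table 6-8 keeps everolimus at 5 mg. Result: 200 mg + 5 mg, change 0.
- Recurrent grade 3 thrombocytopenia: this row does not name ribociclib. With everolimus held constant and exemestane not reducible, only ribociclib is left to step down. Result: 200 mg + 5 mg, change 0.
- QTcF 481-500 ms: the row names ribociclib. One step or two steps give 200 - 200 = 0 mg reduction.

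The row for QTcF of 501 ms or more reduces study treatment as a whole, so it works with Table 6-6 and is not part of the conflict.

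**Step 3. Other sources of a lower level.** Section 6.2 fixes ribociclib at 200 mg for cohort C. Table 6-7 lists 200 mg three weeks on, one week off, but only when everolimus is held more than 3 weeks for pneumonitis. Table 6-5's relative steps, if borrowed, would give 200 - 50 = 150 mg (-25%), then 150 mg on 21 of 28 days; its title does not cover these patients.

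**Step 4. Patients on this schedule.** Group 2: 33 (SAP Section 4). Cohort C: 25 Phase I patients at Amendment 3 minus 18 at Amendment 2 = 7, assuming those 18 were all in cohorts A and B. Total 33 + 7 = 40. Phase II enrolment at Amendment 3 was 79 = 46 + 33, so Group 2 was already recruited by then.

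**Step 5. How often the triggers might occur.** No rate is given for continuous 200 mg + 5 mg. The nearest data are grade 3/4 counts in Table 1-6 for the same doses given three weeks on, one week off, fed, n = 6. Clopper-Pearson 95% limits solve P(X ≥ x | p) = 0.025 and P(X ≤ x | p) = 0.025:

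- Neutropenia 2/6: 4.3-77.7%. Neutrophil count decreased 1/6: 0.4-64.1%. Whether these are different patients is not stated.
- Thrombocytopenia 0/6 and platelet count decrease 0/6: 0-45.9% each.
- QT prolongation 0/16 at 250-300 mg continuous (Section 1.2.5.1.2): 0-20.6%.

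Grade 4 is not shown separately and the schedule differs, so these intervals do not establish a trigger rate.

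**The case against.** The strongest reply is that a coherent reading exists. Section 6.4.1.1 speaks of each patient, refers to Table 6-5 for ribociclib levels, and then refers to both tables for study treatment. A site could use Table 6-5's relative steps where a rule names ribociclib and Table 6-6 where a rule names study treatment. That stands to this extent: the text is contradictory rather than unworkable, and a restart at an unchanged dose is one reading, not the only one. It does not remove the conflict, because Table 6-5 is titled for other patients and Table 6-6 has its own ribociclib column.

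Reading a dose level as the whole Table 6-6 row does not help either: the QTcF row names ribociclib, and the two blood-count rows hold everolimus.

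Other points are fair. Most toxicity rows refer to study treatment, or do not fix everolimus, and work with Table 6-6. The 200 mg floor was planned for cohort C. The sentence barring everolimus reductions dates from Amendment 1, before cohort C existed, so it is probably leftover wording. Section 1.2.1.4.1 places the onset of QT changes and neutropenia in the first cycle, so a correction now reaches only patients still on treatment. Both drugs are held until recovery, and ECGs are repeated 7 and 14 days after a QTcF restart. These points limit the consequence but do not reconcile the tables.

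**Conclusion.** The inconsistency is real and should be fixed. Three rules require a lower ribociclib dose, and the table written for cohort C and Group 2 offers a change of 0 mg at both steps. About 40 patients were assigned the schedule, on the Step 4 assumption about cohorts A and B. Those affected are the patients who reach a trigger and restart; the documents do not allow that number to be estimated. The consequence is for patient safety at restart. The analysis of clinical benefit rate does not change.

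Two smaller slips in the same rules are separate from this conclusion. Section 7.2.2.6.1 sends QTcF of 481 ms or more to Table 6-7, the pneumonitis table, instead of Table 6-9. In Table 6-11, AST or ALT above 10 and up to 20 x ULN falls both in grade 3 (interrupt and reduce) and in the row labelled grade 4 (discontinue).

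**What to change.** 1. In Table 6-6, give an explicit action for the three rules: either ribociclib steps, for example 150 mg daily and then the current dose on 21 of 28 days (50 mg units are supplied, Table 6-1), or a statement that treatment stops. State which toxicities lower ribociclib and which lower everolimus.
2. Limit the Section 6.4.1 sentence barring everolimus reductions to cohorts A/B and Group 1, and align the paragraph after Table 6-6 with it.
3. Change the reference in Section 7.2.2.6.1 from Table 6-7 to Table 6-9.
4. Make the AST/ALT bounds in Table 6-11 non-overlapping: grade 4 above 20.0 x ULN, or grade 3 capped at 10.0 x ULN.

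The choice in item 1 is clinical and belongs to the sponsor. Ribociclib 150 mg + everolimus 5 mg is not among the doses in Tables 1-5 to 1-7, and a lower ribociclib dose also lowers everolimus exposure, which Group 2 was set up to maximise; stopping treatment avoids both. The cost is amendment wording and an investigator letter, with no added visits, procedures, patients or drug strengths.
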